7.6.4 Subgroup analyses

Subgroup analyses using descriptive statistics of the following endpoints may be presented if considered feasible: change from baseline for eGFR, change from baseline for total and free plasma oxalate concentration, change from baseline for 24h urine oxalate excretion (non-centrifuged only), stone events incidence rate (as per adjudicated data) and change from baseline for speckle tracking and traditional echocardiography (limited to LVEF/GLS). Presentations will be done for each visit. Both baselines will be used. The analyses will be based on the following subgroups, provided the subgroups are sufficiently large (>2):

- Subjects with a baseline urinary oxalate excretion (non-centrifuged) above and equal to or below 1.87 mmol/L/24h/1.73 m² respectively (mean of the two values during screening/baseline of the ePHex study).
- Subjects above or equal to and below 18 years of age at baseline of the ePHex study.
- Subjects with a baseline eGFR above or equal to (\geq) and below ($<$) 60 ml/min/1.73m² respectively (mean of the obtained values during screening/baseline of the ePHex study calculated by the Schwartz/CKiD equation⁴), with correction for 18-23 years.
- Race.
- Gender.
- Progressors and non-progressors (see section 11.1) based on historical eGFR (i.e. eGFR prior to treatment start including the baseline/screening values of the ePHex study), using the Schwartz/CKiD equation.

⁴ The Schwartz CKiD 2009 creatinine-based “bedside Schwartz” equation for children (below 18 years of age) and 2009 creatinine-based CKD-EPI equation for adults.

For the subgroup analyses only the FAS population will be used. No formal testing of subgroups will be performed due to small sample sizes. No plots will be created.

7.7 Safety and tolerability evaluation

The safety population is used for all safety presentations. All summaries will be presented for the overall group and per treatment as randomised during the ePHex study. Where change from baseline is mentioned, this refers to the baseline of the ePHex study.

Note that all data collected are presented in listings as well, and safety listings will be presented including subject number, treatment ((O - O) and (P - O)), and age, race and sex as collected during baseline of ePHex-OLE.

If applicable, laboratory safety data collected as additional/unscheduled assessments (i.e. apart from those per protocol) will only be listed and will not be used in summary statistics.

Study phase will be added to the AE and prior/concomitant medication presentations. Study phase will be defined for ePHex-OLE as: baseline (meaning pre-treatment of ePHex-OLE), treatment, safety follow-up and post safety follow-up, using the applicable ADaM domain with manipulation to obtain the post follow-up phase from STDM domain EPOCH. The post follow-up phase is the phase following the four-week safety follow-up after the last dose of study treatment. Post follow-up data will only be presented in listings and not taken into consideration in any descriptive statistics.

7.7.1 Adverse events

Treatment emergent adverse events (TEAE) are defined as adverse events reported on or after first dose of study treatment during ePHex-OLE study and up to the end of the safety follow up phase, being 4 weeks after last dose of open label medication in the study. All AEs reported in the study will be listed.

Kidney stone events are also collected as part of the CRF AE pages and, although included as a key secondary efficacy assessment, will also be included in the AE safety analyses as described in this section.

A TEAE overview table will be created displaying the number of subjects (and percentage) experiencing a treatment-emergent adverse event (TEAE) and the number of TEAEs for: any TEAE, any TEAE per severity grade (1-5, per CTCAE version 4.0), any related/unrelated TEAE, any SAE, any Fatal AEs/Deaths during study and any TEAE leading to study discontinuation. Tabulation will be done by treatment group and overall.

All TEAEs are tabulated by System Organ Class (SOC) and Preferred Terms (PTs) within each SOC according to the MedDRA terminology list. TEAEs will also be tabulated by severity grade (1-5, per CTCAE version 4.0) and by relationship to study medication (related/unrelated), using frequency counts (number of subjects with at least one event, and number of events) and percentage of subjects with the event. Similar tables will be created for TEAEs leading to premature discontinuation, SAEs and fatal AEs/deaths, if applicable. All summary tables will be presented by decreasing frequency of occurrence based on SOC and PT.

The summary tables will be accompanied by individual subject listings of *all* reported AEs including information on AE number, actual AE description, date/time of start and end of AE (or ongoing), treatment-emergent (as in: present on or after first dose), PT (MedDRA), SOC

(MedDRA), severity grade, relationship, seriousness, action taken and outcome. Pre-existing AEs are not considered to be treatment-emergent, except in case of worsening during/after study treatment (to be collected as separate AE in the database). AEs starting prior to administration of the study drug will only be included in the AE listing. In this listing, a clear distinction will be made between prior and treatment emergent events. Day and phase will be added as well.

Separate listings will be created for SAEs and deaths, if applicable.

For summary tables, an AE is considered related if the causality to the study medication is classified as either ‘Certain’, ‘Probably/likely’, ‘Possible’, ‘Unclassifiable’ or missing. In other instances, the AE will be considered unrelated for summary tables. The original causality description will be used in listings, and a footnote will be added to the summary tables to explain the classification.

7.7.2 Clinical laboratory

The following laboratory safety data are collected for this study:

Haematology	Chemistry	Urinalysis
RBC (Erythrocytes)	Blood Urea Nitrogen	Protein
WBC (Leucocytes)	Electrolytes (Na ⁺ , K ⁺ , Mg ⁺⁺ , Ca ⁺⁺ , HCO ₃ ⁻ , Cl ⁻)	Glucose
Lymphocytes	Glucose	pH
Monocytes	Albumin	
Neutrophils	Alkaline phosphatase	
Basophils	ALT	
Eosinophils	AST	
Platelets	Total bilirubin	
Haemoglobin		
Haematocrit		
MCV		
MCHC		

Urine 24h measurements are already presented as ‘Other endpoints’ markers for renal function, renal tubular capacity and inflammation (see section 7.6.3).

Laboratory safety data for haematology, biochemistry and urinalysis will be summarized using descriptive statistics for values over time, change from baseline and percent change from baseline per visit and treatment group/overall, using protocol visits. Listings will include the change from baseline values.

Safety laboratory parameters are collected both in conventional units and SI units: SI units will be used in the tabular presentations.

Lastly, for clinical laboratory parameters, a listing will be created presenting all data that are out of reference range on a per-subject level, including any available unscheduled measurements. The investigator has judged the out-of-range values on their clinical significance, and this information will be added as well. Information regarding age at screening and gender will be added to this listing.

7.7.3 Vital Signs

Vital sign data consist of measurements for pulse rate, systolic and diastolic blood pressure, body temperature and respiration rate. Vital signs will be summarized and listed per visit and per treatment group, using protocol visits and metric units (see section 11.1). Change from baseline will be calculated and presented as well, using the same summary statistics. If applicable, vital sign measurements collected as additional/unscheduled assessments (i.e. apart from those per protocol) will only be listed and will not be used in summary statistics.

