11.7 Vital Sign Measurements

Vital sign measurements on study include temperature and blood pressure (systolic and diastolic in a supine position), heart rate, respiratory rate (assessed after 5 minutes resting in a supine position), weight and height. Weight will be measured using a calibrated scale with the subject lightly clothed and shoes off. Height will be measured using a calibrated wall mounted stadiometer. Height should be measured at each visit for all patients where the Schwartz equation is used to determine eGFR. This would apply to children (patients under 18 years of age at the screening visit of the ePHex study) and to any patient who turn 18 either during the ePHex study or the ePHex-OLE study periods. For patients who are adults at the screening visit of the ePHex study, height for the ePHex-OLE study will be retrieved from the ePHex database using the subject ID.

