12.9 Safety

Adverse events will be categorised by System Organ Class (SOC) and Preferred Term from MedDRA. Safety data will be summarised for the overall study population SAF and also according to the actual treatment received in the ePHex study 0-0 and P-0. AEs will be considered to be treatment emergent if the event occurs on or after the first administration of open label Oxabact treatment and up to 4 weeks after the last dose date of open-label Oxabact treatment of the ePHex-OLE study.

The incidence of AEs will be summarised using descriptive statistics, by SOC, preferred term and severity grade (CTCAE) for all treatment emergent, serious, treatment-related, and serious treatment-related AEs. Summaries will be provided separately for AEs leading to investigational product discontinuation and deaths (severity grade 5).

Changes in safety laboratory parameters, vital signs and physical examinations will also be summarised. Graphical representations may also be presented for parameters of interest. Listings of SUSARs, AEs and SAEs will be provided along with narratives.

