7.5.1 Demographics

Data (including weight, height and BMI measurements at screening) for FAS and SAF per treatment group and overall will be summarized, using metric units where applicable (see section 11.1 for reference to addendum). Appropriate descriptive statistics for age, height, weight, BMI, race and sex will be given.

Demographics in the ePHex study and in the ePHex-OLE study will be described for the subjects enrolled in the ePHex-OLE study. Demographics will also be described for subjects included in the FAS of the ePHex study, but not participating in the ePHex-OLE study.

The listing of demographic data will include information on childbearing potential (for females only).

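### SAP 7.7.3 drops weight and height from the protocol's vital-sign summaries without declaring it, so no summary of either is planned during open-label treatment

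*SAP*

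**What the plan says.** **Protocol.** Section 11.7 ends its list of vital signs with "respiratory rate (assessed after 5 minutes resting in a supine position), weight and height". On height it adds: "Height should be measured at each visit for all patients where the Schwartz equation is used to determine eGFR". It applies this to subjects under 18 at ePHex screening and to anyone who turns 18 during either study; for subjects already adult at ePHex screening, height is taken from the ePHex database. Table 5 and section 6.3.2 schedule vital signs at every clinic visit. Section 12.9 states: "Changes in safety laboratory parameters, vital signs and physical examinations will also be summarised".

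**SAP.** Section 7.7.3 opens: "Vital sign data consist of measurements for pulse rate, systolic and diastolic blood pressure, body temperature and respiration rate". It then plans summaries, change from baseline and listings for those data, and Table 14.3.5 carries the result. Weight and height are summarised only under 7.5.1: "Data (including weight, height and BMI measurements at screening) for FAS and SAF per treatment group and overall will be summarized". Section 7.6.1 uses children's height at each visit as an input to eGFR. Section 8 lists several changes from the protocol; none concerns vital signs or safety grouping.

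**Grouping of safety data.** Protocol 12.9 presents safety overall and also "according to the actual treatment received in the ePHex study". SAP 7.7 says: "All summaries will be presented for the overall group and per treatment as randomised during the ePHex study".

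**The concern.** Additional safety data are the study's only secondary objective (Protocol 5.2). The parent study enrols from age 2 (Protocol 4.4.1.8), and open-label treatment lasts two years. Weight in all subjects, and height in those still growing, are collected at each visit and are natural cumulative safety measures over that time. The protocol promised that change in them would be summarised. If the SAP is programmed as it stands, that output will not exist, and nothing in section 8 tells the reader of the study report that it was dropped.

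Height also feeds the children's eGFR through the Schwartz formula (SAP 7.6.1), so a by-visit height summary would help in reading the primary endpoint.

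The grouping mismatch raises a different and smaller issue. A subject given the wrong ePHex treatment would be placed in the wrong previous-exposure group in the safety tables.

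**Working it through.** No alpha, power or effect size is involved. The check sets the two documents side by side.

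| Vital-sign item | Protocol 11.7 | SAP 7.7.3 |
|---|---|---|
| Temperature | yes | yes |
| Systolic blood pressure | yes | yes |
| Diastolic blood pressure | yes | yes |
| Heart (pulse) rate | yes | yes |
| Respiratory rate | yes | yes |
| Weight | yes | no |
| Height | yes | no |

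The SAP keeps 5 of 7 items.

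1. **Is a summary of change promised?** Yes. Protocol 12.9 covers vital signs, and Protocol 11.7 defines what they are.
2. **Is it supplied elsewhere in the SAP?** No. The summary in 7.5.1 is a demographic one. Even though it describes demographics for both studies, nothing in it falls after the first open-label dose. Height in 7.6.1 is an input to a formula and is not tabulated.
3. **Are the values listed?** They should be. SAP 7.1, 7.7 and 12.4 all say that collected data will be listed individually, although 7.7.3 does not name weight or height for the vital-sign listing.
4. **Is the change declared?** No. Section 8 covers additions for plasma oxalate, the PH-type subgroup, the pattern-mixture analysis and the regression slopes.
5. **How many records?** There are 10 visits after Month 0: six in year 1 (months 2 to 12) and four in year 2 (months 15 to 24). SAP 2.4 gives 18 subjects. The ceiling for weight is 10 x 18 = 180. At the planned drop-out of 25% per year, with all losses placed at the start of each year as a worst case, 18 x 0.75 = 13.5 and 13.5 x 0.75 = 10.125 subjects remain. That gives 6 x 13.5 + 4 x 10.125 = 81 + 40.5 = about 122. The range is therefore about 122 to 180. The number of height records cannot be given, because the documents do not say how many of the 18 are children.
6. **Which baseline would a change table use?** SAP 7.1 says safety parameters use only the second baseline, and defines that baseline only for subjects who had placebo in ePHex. SAP 7.7 says that change in the safety section refers to the ePHex baseline. These conflict, and under 7.1 read literally the O-O group has no safety baseline.
7. **Grouping.** Protocol 6.2 defines O-O and P-O by randomisation. Protocol 12.3 uses those groups for summaries, but assigns safety analyses by treatment received in ePHex-OLE, which is Oxabact for everyone and cannot separate the groups. Protocol 12.9 uses treatment actually received in ePHex. SAP 7.7 uses randomised treatment. If the 18 split evenly (an assumption), one misallocated subject is 1/9 = 11% of a group.

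**The case against.** The strongest reply is that nothing is hidden. Per-subject listings should hold every weight and height, and in a study of 18 subjects a reader can follow individuals from a listing. The protocol's stated reason for measuring height at each visit is the Schwartz equation, not growth monitoring. The named risks have their own measures: bicarbonate for acidosis and adverse-event tables for gastrointestinal symptoms. Cells would be small; two treatment groups by two age bands average 18/4 = 4.5 subjects at entry. Addendum 1 (SAP 11.1), which is not among the documents, might also add handling of these data.

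Much of this stands. A reader might infer that growth in treated children is never reported; the listing rules and the screening summary rule that out. A reader might also infer that weight and growth are the measures most likely to reveal slow harm; no section of either document says so. The protocol asks for neither on-study BMI nor growth curves.

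What does not stand is the idea that a listing meets a commitment to summarise change. SAP 7.7.3 refers to section 11.1 beside metric units, not for further parameters.

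On grouping, SAP 7.7 agrees with the definition in Protocol 6.2, so this is not simply the SAP departing from a clear rule. The protocol disagrees with itself. Grouping also has no bearing on whether weight or height is reported.

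**Conclusion.** The point holds in this form. SAP 7.7.3 omits two of the seven vital-sign items in Protocol 11.7, Protocol 12.9 required their change to be summarised, and section 8 does not declare the omission. No summary or change from baseline in weight or height is planned during open-label treatment; about 122 to 180 weight records, and an unknown number of height records, would appear only in listings. This is a missing protocol-specified safety output. It affects no efficacy conclusion. It rests on the SAP text alone and would fall if Addendum 1 already restores these parameters.

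The grouping mismatch is real and undeclared but minor. It alters a safety table only if a subject received the wrong ePHex treatment, none is documented, and safety is also shown for all subjects together.

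**What to change.** 1. In SAP 7.7.3 and Table 14.3.5, add weight for all subjects, and height for those measured at each visit under Protocol 11.7 (under 18 at ePHex screening, or turning 18 on study). Give observed values and change from baseline by visit, with those subjects shown separately. By-visit height for subjects already adult at ePHex screening should be left out, since it is not remeasured. If the sponsor prefers not to add these summaries, declare and justify the omission in section 8.
2. State one safety baseline and use it in both SAP 7.1 and SAP 7.7. It must be defined for the O-O group as well as the P-O group.
3. Minor: align the safety grouping in SAP 7.7, and the general as-randomised rule in SAP 7.1 where it reaches safety tables, with Protocol 12.9. Reconcile Protocol 6.2, 12.3 and 12.9 so that one rule assigns subjects to O-O and P-O for safety.

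The cost is SAP wording and an extension of one planned table, from data already collected, plus a clarification of the protocol text for item 3. No new visit or measurement is needed.

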7.7.4 Prior and concomitant medication

The use of prior and concomitant medication will be listed for all subjects: included will be the medication generic name, WHO coding information, dose, route of administration, start and stop date, study day and study phase, frequency and reason for administration, as well as information if given for an AE/MH. A differentiation (flag) will be made between prior and concomitant medication.

In addition, frequency tables for prior and concomitant medications will be created, presenting the number of subjects with any prior/concomitant medication, and the number of subjects for each ATC System Pharmacological/Therapeutic group (2nd level of WHO classification) and the Chemical Substance (5th level of WHO classification), irrespective of duration of receipt, frequency or dose. The presentation will be done per treatment group and overall.

A separate summary will present concomitant medications starting or ongoing at Day 1 (first dose date of investigational medicinal product).

If a medication is started prior to first dose of open-label treatment in the ePHex-OLE study, this is considered prior medication. Concomitant medication is defined as started before first open-label treatment in the ePHex-OLE study and continuing thereafter or starting on/after first dose date of open-label treatment in the ePHex-OLE study. As a consequence, several medications may be defined both as prior as well as concomitant. Whether a medication is considered prior/concomitant/both in case of partially missing start dates is determined using the rules for missing data detailed in Section 7.2. Furthermore, considering the data integration necessary to include the ePHex data, further details on prior medication are provided in the document referred in section 11.1.

7.7.5 Physical examination

General physical examination data will be tabulated and listed. The summary table will include number/percentage of subjects with normal or abnormal observations and NCS/CS frequencies/percentages for abnormal observations.

7.8 Scheduled visits, Dosing and Treatment Compliance

7.8.1 Visit dates

A listing with actual visit dates (and times, if applicable) per subject will be presented. This listing will include study day information as well.

7.8.2 Dosing and drug accountability

Relevant dosing information (first dosing date, last dosing date, missed doses), scheduled and actual dosing dates/times and drug accountability (total dispensed and returned medication) will be listed for each subject.

8 CHANGES FROM PROTOCOL AND OTHER RELEVANT REMARKS

The descriptive statistics on percent change from baseline in total plasma oxalate concentration, on subjects achieving 'near-normalization' of total plasma oxalate concentration (<10 µmol/L), and on the shifts to minimum and maximum values for total plasma oxalate concentration were not mentioned in the protocol, but added as these were considered relevant in the ePHex study.

Subgroup analysis based on type of PH (as per randomization for ePHex) will not be conducted due to the expected insufficient number of subjects in the subgroups.

The sensitivity analysis for the MRMM for eGFR will be done under the assumption of missing at random (MAR). Since it concerns a supportive analysis of the descriptive statistics with a small sample size, no further analysis will be done to assess the robustness of the primary analysis to possible deviations from the missing at random (MAR) assumption, and therefore the pattern-mixture analysis is removed from the SAP.

Furthermore, the regression analysis to determine slopes for eGFR, and the summary table and statistical thereof is excluded from the SAP, considering slopes are already determined based on a MRMM. Any apparent differences in slopes can best be assessed based on the individual slope results of the MRMM analyses and viewing the spaghetti and mean plots.

Any post-hoc analyses or changes in regards to the statistical analysis plan when performing the final analyses after data base lock, will be captured in a Note to File and used for the relevant sections in the clinical study report.

9 COVID-19 DETAILS

This study is conducted during the Covid-19 outbreak. A number of data capture decisions are taken due to national, local, or site-specific restrictions imposed due to Covid-19, with the primary need to prioritize the safety of clinical study teams and subjects, and to maintain the integrity of the study/data collection.

The impact of the Covid-19 outbreak on the data and the proposed statistical analyses is detailed in a separate document (Addendum 2), which will be maintained as a living document throughout the study continuation and is dependent on the duration and impact of the Covid-19 situation. The document will be finalized during DRM, prior to database lock and unblinding.

